## 7. HANDLING OF MISSING VALUES

For the analysis of safety endpoints, the sponsor data standard rules for imputation will be applied.

### 7.1. Concentrations below the Limit of Quantification

In summary statistics for pharmacokinetic assayed values below the lower limit of quantification (LLOQ) will be set to zero. The imputations (eg,  $\frac{1}{2}$  LLOQ) may be considered in other analyses (eg, Pop-PK, PK/CCI, and CCI [REDACTED]), if deemed appropriate. In listings values below LLOQ will be reported as “<LLOQ” where LLOQ will be replaced with the numerical value for the lower limit of quantification. The LLOQ for various PK and CCI concentrations will be noted in all tables and listings.

### 7.2. Deviations, Missing Concentrations and Anomalous Values

In summary tables and plots of median profiles, statistics will be calculated having set concentrations to missing if one of the following cases is true:

1. A concentration has been collected as ND (ie not done) or NS (ie no sample),
2. A deviation in sampling time is of sufficient concern or a concentration has been flagged anomalous by the pharmacokineticist.

Note that summary statistics will not be presented at a particular time point if more than 50% of the data are missing.

### 7.3. Pharmacokinetic Parameters

Actual PK sampling times will be used in the derivation of PK parameters.

If a PK parameter cannot be derived from a subject’s concentration data, the parameter will be coded as NC (ie not calculated). (Note that NC values will not be generated beyond the day that a subject discontinues).

In summary tables, statistics will be calculated by setting NC values to missing; and statistics will be presented for a particular dose with  $\geq 3$  evaluable measurements.

If an individual subject has a known biased estimate of a PK parameter (due for example to an unexpected event such as vomiting before all the compound is adequately absorbed in the body), this will be footnoted in summary tables and will not be included in the calculation of summary statistics or statistical analyses.

## 8. STATISTICAL METHODOLOGY AND STATISTICAL ANALYSES

While every effort has been made to pre-specify all analyses in this statistical analysis plan, should [REDACTED], the analyses and the reasons for them may be detailed in the clinical study report. In all data presentations, results will be sorted by increasing dose level, starting with Placebo.

### 8.1. Sample Size Determination

#### 8.1.1. Healthy Subject Single Ascending and Multiple Dose

*A sample size of 8 subjects in each SAD and MAD cohort (with 6 active and 2 placebo) with approximately 48 subjects (assuming 6 cohorts) and 24 subjects for optional cohorts MAD BID cohort, Cohort 7 and 8 is not based on any statistical considerations. Sample size for optional Japanese subject cohort is not based on any statistical considerations, and may enroll up to 8 subjects in order to support characterization of the PF-06826647 PK profile in Japanese subjects. The sample size was based on the clinical consideration to provide safety and tolerability information and pharmacological considerations and on the need to minimize exposure to healthy subjects at each dose level. No formal inferential statistics will be applied to the safety, pharmacodynamic or pharmacokinetic data.*

#### 8.1.2. Psoriasis Multiple Dose

*A sample size of approximately 42 subjects total is planned for the two psoriasis cohort(s). Psoriasis subjects will be randomized in each Psoriasis cohort to receive either active PF-06826647 (or placebo) with a planned randomization ratio of 2:1 (PF-06826647:Placebo) for each cohort. The between-subject standard deviation of absolute PASI change from baseline to Day 28 (obtained from Sponsor data on file) is assumed to be 8. The true difference between PF-06826647 and placebo is assumed to -7.8 (derived from the meta-analysis of the Tofacitinib data). Based on these assumptions the sample size is calculated to be 14 subjects per arm to provide approximately 80% power. This calculation assumes a one-sided alpha of 5%. The initial estimate of the total number of completers for the psoriasis cohort will be 42 with 21 (14 active + 7 placebo) in each cohort. Based on the results from the planned interim analysis (described in Section 9.7 of the protocol) PF-06826647 dose level or regimen may be adjusted for subsequent psoriasis subjects/cohorts enrolled after the interim analysis.*

The exact confidence interval of a binomial proportion will be computed due to Blyth-Still-Casella (Casella (1986)). The estimated risk difference and the associated confidence interval of the risk differences will be computed based on the unconditional exact method proposed by Chan and Zhang (1999).

The sample SAS code for analysis of binary data is presented in [Section 9.2](#).

### 8.3. Statistical Analyses

#### 8.3.1. Pharmacokinetic Analysis

##### 8.3.1.1. Pharmacokinetic Parameters

To assess the pharmacokinetics of PF-06826647, the PK parameters detailed in [Section 6.4](#) will be listed and summarized for subjects in the PK analysis set (as defined in [Section 5.2](#)). Missing values will be handled as detailed in [Section 7](#). Each PK parameter will be summarized by dosing regimen and period, and will include the set of summary statistics as specified in the table below:

**Table 1. PK Parameters to be Summarized Descriptively**

Parameter	Summary Statistics
AUC last , AUC inf , C max , AUC last(dn) , AUC inf(dn) , C min , C av , AUC τ , C max(dn) , R ac , R ac , C max , PTR, CL/F, and V Z /F, Ae τ , Ae τ % and CL r	N, arithmetic mean, median, cv%, standard deviation, minimum, maximum, geometric mean and geometric cv%.
T max	N, median, minimum, maximum.
MRT and t 1/2	N, arithmetic mean, median, cv%, standard deviation, minimum, maximum.

There will be 1 summary table presenting all PK parameters. This will include data from all cohorts and will be paged by cohort. The treatment subheading will include the cohort number and dosing regimen information.

To assess the relationship between the PK parameters and dose, dose normalized AUCinf, AUClast and Cmax will be plotted against dose (using a logarithmic scale), and will include individual subject values and the geometric means for each dose. Geometric means will have a different symbol than the individual values. The values will be dose normalized (to a 1 mg dose) by dividing the individual values and raw geometric means by dose. A footnote will be added to the plots to indicate that geometric means are presented and that data from both cohorts are presented on the plot.

Natural log transformed AUCinf (if data permit), AUClast and Cmax will be analyzed using a mixed effect model with dose as a fixed effect and subject as a random effect, for all cohorts in healthy volunteer; the similar exercise will be completed with patient cohort separately.

The purpose of these analyses is to obtain estimates of the intra-subject variation to assist in the planning of future studies. No treatment contrasts will be provided.

Supporting data from the estimation of  $t_{1/2}$  and  $AUC_{inf}$  will be listed by analyte where applicable: terminal phase rate constant ( $k_{el}$ ); goodness of fit statistic from the log-linear regression ( $r^2$ ); the percent of  $AUC_{inf}$  based on extrapolation ( $AUC_{extrap\%}$ ); and the first, last, and number of time points used in the estimation of  $k_{el}$ . This data may be included in the clinical study report.

Presentations for PF-06826647 concentrations will include:

- a listing of all concentrations sorted by subject ID, cohort, dose and nominal time post-dose. The concentration listing will also include the actual times. Deviations from the nominal time will be given in a separate listing.
- a summary of concentrations by cohort, dose and nominal time post-dose, where the set of statistics will include n, mean, median, standard deviation, coefficient of variation (cv), minimum, maximum and the number of concentrations above the lower limit of quantification.
- median concentrations time plots (on both linear and semi-log scales) against nominal time post-dose by cohort and dose (all treatments on the same plot per scale, based on the summary of concentrations by cohort, dose and time post-dose).
- Median concentration time plots (on both linear and semi-log scales) against nominal time post-dose by meal condition and dose for Day 1 (0-24 h post dose) for Cohort 3, 4 and 5 (30, 100 and 400 mg cohorts).
- Boxplot of dose-normalized  $AUC_{24}$  and  $C_{max}$  on Day 1 in SAD and MAD separately by dose group and meal condition for Cohorts 3, 4 and 5.
- mean concentrations time plots (on both linear and semi-log scales) against nominal time post-dose by cohort and dose (all treatments on the same plot per scale, based on the summary of concentrations by cohort, dose and time post-dose).
- individual concentration time plots by cohort and dose (on both linear and semi-log scales) against actual time post-dose (there will be separate spaghetti plots for each dose per scale).
- individual concentration time plots by subject (on both linear and semi-log scales) against actual time post-dose [there will be separate plots for each subject (containing all doses) per scale].

The length of time used for the x-axes of these plots will be decided on review of the data, and will depend on how long PF-06826647 concentration is quantifiable in the matrix.

For summary statistics, median and mean plots by sampling time, the nominal PK sampling time will be used, for individual subject plots by time, the actual PK sampling time will be used. All statistical analyses related to the CCI will be performed as stated in Section 6.4.

CCI [Redacted]

CCI [Redacted]

[Redacted]

**8.4. Safety Analysis**

For each of SAD/MAD (healthy volunteer cohort) and Psoriasis cohort a set of summary tables split by treatment will be produced separately to evaluate any potential risk associated with the safety and toleration of administering PF-06826647.

No formal analyses are planned for safety data. The safety and other endpoints detailed in [Section 6.2](#) will be listed and summarized in accordance with sponsor reporting standards, where the resulting data presentations will consist of subjects from the safety analysis set.

#### **8.4.1. Treatment and Disposition of Subjects**

Subject evaluation groups will show end of study subject disposition and will show which subjects were analyzed for pharmacokinetics, as well as for safety (adverse events and laboratory data). Frequency counts will be supplied for subject discontinuation(s) by treatment.

Data will be reported in accordance with the sponsor reporting standards.

#### **8.4.2. Demographic and Clinical Examination Data**

A breakdown of demographic data will be provided for age, race, weight, body mass index and height. Each will be summarized by cohort and Overall in accordance with the sponsor reporting standards.

#### **8.4.3. Discontinuation(s)**

Subject discontinuations, temporary discontinuations or dose reductions due to adverse events will be detailed and summarized by treatment.

Data will be reported in accordance with the sponsor reporting standards.

#### **8.4.4. Adverse Events**

Adverse events will be reported in accordance with the sponsor reporting standards.

#### **8.4.5. Laboratory Data**

Laboratory data will be listed and summarized by treatment in accordance with the sponsor reporting standards.

Mean change from baseline will be plotted against nominal time post dose. On each plot there will be one line for each treatment. The placebo data from all cohorts (for the SAD/MAD and Psoriasis cohorts) period will be plotted on the same figure using separate lines. Individual plots of changes from baseline will also be produced for each cohort and treatment.

#### **8.4.6. Vital Signs Data**

Absolute values and changes from baseline in supine systolic and diastolic blood pressure and pulse rate will be summarized by cohort, treatment and time post-dose, according to sponsor reporting standards. Tables will be paged by parameter. Baseline is as defined in [Section 6.3.3](#).

Mean changes from baseline for supine systolic and diastolic blood pressure and pulse rate will be plotted against time post-dose. On each plot there will be separate line for each

treatment. Data from all cohorts will be plotted on the same figure using separate lines for different placebos. Corresponding individual plots of changes from baseline will also be produced for each cohort and treatment.

For supine systolic and diastolic blood pressure and pulse rate, the differences between each dose and placebo (dose – placebo) will be summarized (N, mean, 90% confidence interval) and plotted (mean) for each cohort, dose and timepoint (including baseline).

Maximum absolute values and changes from baseline for vital signs (for supine) will also be summarized descriptively by treatment. Numbers and percentages of subjects meeting the categorical criteria will be provided. All planned and unplanned post-dose timepoints will be counted in these categorical summaries. All values meeting the criteria of potential clinical concern will be listed.

#### **8.4.7. ECG Data**

Absolute values and changes from baseline in QT, heart rate, QTcF, PR and QRS will be summarized by cohort, treatment and time post-dose using sponsor reporting standards. Tables will be paged by parameter. Baseline is as defined in [Section 6.3.4](#).

Mean changes from baseline in QT, heart rate and QTcF will be plotted against time post-dose. On each plot there will be 1 line for each treatment. Data from all cohorts will be plotted on the same figure using separate lines for different placebos. Corresponding individual plots of changes from baseline will also be produced for each cohort and treatment.

Changes from baseline in QTcF will also be plotted separately against drug concentrations. This will be a scatter plot for all observations where QTcF and drug concentration are recorded. Placebo data will also be included (with drug concentration set to zero). Different symbols will be used for each treatment. There will be 1 plot for each cohort.

Maximum increase from baseline for QTcF, heart rate, QT, PR and QRS will be summarized by cohort and treatment, according to sponsor reporting standards.

In addition for QTcF, heart rate and QT, the differences between each dose and placebo (dose – placebo) for each subject will be summarized and plotted (N, mean, 90% confidence interval) for each cohort, dose and timepoint (including baseline).

ECG endpoints and changes from baseline (QTcF, PR and QRS) will also be summarized descriptively by cohort and treatment using categories as defined in [Section 9.4](#) (for QTc these correspond to ICH E14). Numbers and percentages of subjects meeting the categorical criteria will be provided. All planned and unplanned post-dose timepoints will be counted in these categorical summaries. All values meeting the criteria of potential clinical concern will be listed.

Listings of subjects with any single post-dose value  $\geq 500$  msec will also be produced for QTcF.

QTcB will be listed only and not summarized.

**8.4.8. Other Safety Data**

None.

**8.4.9. Concomitant Treatments**

All concomitant medication(s) as well as non-drug treatment(s) will be provided in the listings.

**8.4.10. Screening and Other Special Purpose Data**

Prior medication(s) and non-drug treatment(s), serum FSH concentrations, urine drug screen, serum or urine B-hCG for all females of childbearing potential, and urine or blood cotinine concentration will be obtained at Screening.

## 9. APPENDICES

### 9.1. Definition of Endpoints in Psoriasis Cohort

#### 9.1.1. Psoriasis Area and Severity Index (PASI)

*The Psoriasis Area and Severity Index quantifies the severity of a subjects psoriasis based on both lesion severity and the percentage of body surface area affected. Lesion severity: the basic characteristics of psoriatic lesions - erythema, induration and scaling - provide a means for assessing the severity of lesions. Assessment of these three main signs is performed separately for four areas of the body: head, upper limbs, trunk, and lower limbs. Average erythema, induration and scaling are rated for each body area according to a 5-point scale: 0, no involvement; 1, slight; 2, moderate; 3, marked; 4, very marked.*

*Body surface area (BSA) involvement: the extent (%) to which each of the four areas of the body is affected by psoriasis is assigned a numerical score according to the following area scoring criteria: 0, no involvement; 1, >0 to 9%; 2, 10 to 29%; 3, 30 to 49%; 4, 50 to 69%; 5, 70 to 89%; 6, 90 to 100%.*

#### *Calculating PASI*

*In each area, the sum of the severity rating scores for erythema, induration and scaling is multiplied by the score representing the percentage of this area involved by psoriasis, multiplied by a weighting factor (head 0.1; upper limbs 0.2; trunk 0.3; lower limbs 0.4). The sum of the numbers obtained for each of the four body areas is the PASI.*

$$PASI = 0.1Ah(Eh + Ih + Sh) + 0.2Au(Eu + Iu + Su) + 0.3At(Et + It + St) + 0.4Al(El + Il + Sl)$$

*where A = area of involvement score; E = erythema; I = induration; S = scaling; h = head; u = upper limbs; t = trunk; l = lower limbs*

*The PASI score can vary in increments of 0.1 units from 0.0 to 72.0, with higher scores representing increasing severity of psoriasis.*

**PASI 50/75/90 response rate:** At least 50/75/90% reduction in PASI relative to baseline PASI Score.

#### *Linear-method Psoriasis Area and Severity Index (L-PASI)*

*A second method of calculating PASI will also be performed. A linear-scaling method will be applied to the Psoriasis Area and Severity Index calculation, adapting the classic calculation by using the actual percentage body surface area involved in psoriasis rather than categorizing the percentage involvement on a 7-point scale. The linear-scaling method will be calculated from the study database; investigator sites will only perform the classic PASI calculation during the study. The L-PASI score will be used for a sensitivity analysis.*

*L-PASI Calculation*

$$L-PASI = 0.1(6xBh)x(Eh + Ih + Sh) + 0.2(6Bu)x(Eu + Iu + Su) + 0.3(6xBt)x(Et + It + St) + 0.4(6xBl)x(El + Il + Sl)$$

where *B* = percentage area of involvement; *E* = erythema; *I* = induration; *S* = scaling;  
*h* = head; *u* = upper limbs; *t* = trunk; *l* = lower limbs

CCI

[Redacted]

[Redacted]

[Redacted]

[Redacted]

[Redacted]

[Redacted]

CCI

[Redacted]

[Redacted]

[Redacted]

[Redacted]

[Redacted]

[Redacted]

CCI [Redacted]

CCI [Redacted]

CCI [Redacted]

[figure not shown]
CCI [Redacted]

[Redacted]

[figure not shown]
[Redacted]

[Redacted]

CCI

CCI

[figure not shown]
CCI

CCI

CCI

CCI

## 9.2. SAS Code

### 9.2.1. Continuous Data Analysis

Sample data set ds where for each subject and each visit the following information is stored in the row of the data set.

Id	Subject's id
Cbaseline	Change from baseline
visit	Visit of interest (stored as a categorical)
Trt	Treatment group (stored as a categorical)
Baseline	Baseline observation of the outcome

```
PROC MIXED DATA=<DATA>;
  CLASS ID TRT VISIT;
  MODEL CBASELINE = TRT VISIT TRT*VISIT BASELINE /ALPHA=0.1
DFM=KR;
  REPEATED VISIT /SUBJECT= ID TYPE= UN;
  LSMEANS TRT*VISIT /ALPHA=0.1 CI PDIFF;
  ODS OUTPUT LSMEANS= LSM DIFFS=DIFF COVPARMS=COV;
RUN;
```

### 9.2.2. SAS Code for the Generalized Linear Mixed Model for Binary Longitudinal Data

```
PROC GLIMMIX DATA =<DATA> METHOD=RMPL;
  CLASS SUBJID TRTPN VISIT;
  MODEL RESPONSE (EVENT = "1") = TRTPN VISIT TRTPN * VISIT / ALPHA = 0.1
DIST=BINARY LINK=LOGIT;
  RANDOM VISIT /SUBJECT = SUBJID TYPE=UN RESIDUAL;
  LSMEANS TRTPN * VISIT / ILINK COV DIFF CL;
RUN;
```

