### **9.1.2. Psoriasis Multiple Dose**

A sample size of approximately 42 subjects total is planned for the two psoriasis cohort(s). Psoriasis subjects will be randomized in each Psoriasis cohort to receive either active PF-06826647 (or placebo) with a planned randomization ratio of 2:1 (PF-06826647:Placebo) for each cohort. The between-subject standard deviation of absolute PASI change from baseline to Day 28 (obtained from Sponsor data on file) is assumed to be 8. The true difference between PF-06826647 and placebo is assumed to -7.8 (derived from the meta-analysis of the Tofacitinib data). Based on these assumptions the sample size is calculated to be 14 subjects per arm to provide approximately 80.7% power. This calculation assumes a one-sided alpha of 5%. The initial estimate of the total number of completers for the psoriasis cohort will be 42 with 21 (14 active +7 placebo) in each cohort. Based on the results from the planned interim analysis (described below in [Section 9.7](#)) PF-06826647 dose level or regimen may be adjusted for subsequent psoriasis subjects/cohorts enrolled after the interim analysis.

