### **9.2.1. Analysis of Secondary Endpoints**

The change from baseline in PASI score at Day 28 in the psoriasis multiple dose segment is a secondary endpoint. The treatment effect for each of the test dose groups is the treatment difference in the mean change from baseline of PASI score at Day 28 between the test dose and the placebo. The estimates for treatment effect will be obtained by fitting a repeated measures linear model to the PASI change from baseline score. The model will include treatment (active doses and placebo), week and treatment-by-week interaction as fixed effects and baseline PASI score as a covariate. Estimates and 90% confidence intervals for treatment effect will be presented.

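### The sample GLIMMIX code for binary endpoints sets a 90% level on MODEL but not on LSMEANS, so its model-based limits would print at 95%

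*SAP*

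**What the plan says.** SAP 9.2.2 gives sample code for a generalized linear mixed model for binary longitudinal data. Its MODEL statement carries the interval level: "TRTPN VISIT TRTPN * VISIT / ALPHA = 0.1". The statement that asks for least-squares means, their inverse-link values, their differences and confidence limits reads "LSMEANS TRTPN * VISIT / ILINK COV DIFF CL", with no level.

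SAP 9.2.1, the code for continuous endpoints, sets the level on both statements: "MODEL CBASELINE = TRT VISIT TRT*VISIT BASELINE /ALPHA=0.1" and then "LSMEANS TRT*VISIT /ALPHA=0.1 CI PDIFF".

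For the PASI treatment effect, Protocol 9.2.1 says "Estimates and 90% confidence intervals for treatment effect will be presented". The other levels visible in the documents are also 90%: the pharmacokinetic ratios (Protocol 9.3.1, SAP 6.4), the vital-sign differences from placebo (SAP 8.4.6) and the ECG differences from placebo (SAP 8.4.7).

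The visible text on binary endpoints, which follows SAP 8.1.2, assigns single proportions to the Blyth-Still-Casella exact interval and risk differences to the Chan-Zhang exact method. The templates for these, SAP 9.2.3 and 9.2.4, leave alpha as a placeholder. The same text describes the code as sample code.

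**The concern.** The level that reaches the printed limits is the one on the statement that produces them. In SAP 9.2.2 that statement has none, and the 0.1 that the author wrote sits where it governs only coefficient intervals, which the block does not ask for. A programmer who copies the block would get 95% limits without having chosen them. A missing option is not a syntax error, so it would not by itself raise a warning.

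SAP 4.1 plans no hypothesis testing, so the reader will interpret efficacy through intervals. Model-based response probabilities and odds ratios at 95% would then stand beside PASI change results at 90%, and differences in width that come only from the level could be read as differences in precision.

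**Working it through.** **Assumption about the software.** ALPHA= applies to the statement that carries it, and LSMEANS uses 0.05 when none is given. The documents do not say this. The SAP's own MIXED code is consistent with it, since it repeats the option. No SAS run was made.

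**Where the level is set.**

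| Code block | ALPHA on MODEL | ALPHA on LSMEANS | Resulting level of LS-mean limits |
|---|---|---|---|
| SAP 9.2.1 (MIXED) | 0.1 | 0.1 | 90% |
| SAP 9.2.2 (GLIMMIX) | 0.1 | none | 95% by default |

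**The plan's own figure.** The documents give no figure for the binary model. The only design figure linked to a 90% interval is the power for PASI change. Inputs, from Protocol 9.1.2 and SAP 8.1.2: the standard deviation "is assumed to be 8"; "The true difference between PF-06826647 and placebo is assumed to -7.8"; 14 per arm; and "This calculation assumes a one-sided alpha of 5" percent.

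- Standard error = 8 × √(1/14 + 1/14) = 3.024.
- Noncentrality = 7.8 / 3.024 = 2.58, with 26 degrees of freedom.
- Noncentral t power at one-sided 5% = 80.7%, which is the protocol's figure. At two-sided 5% it would be 70.0%.

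The sizing for PASI change therefore does use one-sided 5%, which corresponds to a two-sided 90% interval.

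**Width on the logit scale.** Estimate and standard error are the same at either level, so the ratio of widths is the ratio of quantiles.

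- Normal: 1.960 / 1.645 = 1.19.
- t quantiles: 1.20 at 39 degrees of freedom, 1.21 at 26 and 1.21 at 18.

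**Illustration.** The responder counts are assumed and are not in the documents: 7/14 on active against 2/14 on placebo, with simple Wald limits on the logit scale.

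- Log odds ratio: estimate 1.79, standard error √(1/3.5 + 1/1.714) = 0.932. At 95%, −0.04 to 3.62; at 90%, 0.26 to 3.33.
- Active rate after back-transformation: at 95%, 26.0% to 74.0% (48.0 points); at 90%, 29.3% to 70.7% (41.4 points). Ratio 48.0/41.4 = 1.16.
- Placebo rate after back-transformation: at 95%, 3.6% to 42.7% (39.1 points); at 90%, 4.5% to 36.9% (32.4 points). Ratio 39.1/32.4 = 1.21.

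On the probability scale, then, the excess depends on the rate: about 16% near one half and about 21% at 2/14.

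**Range.** With assumed active counts from 6/14 to 9/14 against 2/14, the lower limit of the log odds ratio runs from −0.33 to 0.53 at 95% and from −0.03 to 0.82 at 90%. At 6/14 both intervals include zero and at 9/14 both exclude it. At 7/14 the level decides.

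**The case against.** The strongest case against is that this line may not produce the response-rate intervals that get reported. A reader might infer that the PASI 50/75/90 intervals, or the differences in response rate, would come out at 95%. The documents do not support that. Single proportions and risk differences go to the two exact methods, and DIFF in the GLIMMIX step gives log odds ratios, not risk differences. SAP 9.1.1 defines the PASI responses, but no visible text routes them through GLIMMIX. This objection stands, and it limits the point to the model-based output.

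Second, SAP 8.2.2.2 is mostly not visible, and it is where a level for binary endpoints would normally be stated. The 90% intent is inferred from the MODEL line and from the rest of the plan. This also stands. It does not remove the inconsistency: if the hidden text says 90%, LSMEANS fails to deliver it; if it says 95%, the 0.1 on MODEL is the stray value.

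Third, this is sample code, and the comparator is not polished either: it writes `CI` where the GLIMMIX block writes `CL`. That lowers the weight of the point. But sample code in an SAP appendix is there to be reused.

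Fourth, a reader might count the unfilled alpha placeholders in SAP 9.2.3 and 9.2.4 as part of the error. They are missing detail and contradict nothing.

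**Conclusion.** The point holds as a narrow inconsistency in the analysis code. Run as written, the GLIMMIX step would give 95% limits for LS means, back-transformed probabilities and log odds ratios, where its own MODEL line and every visible level in the plan indicate 90%. The limits would be about 19% wider on the logit scale, or 20% to 21% with t quantiles at 39 to 18 degrees of freedom.

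This rests on two assumptions: the SAS default described above, and that the hidden text of SAP 8.2.2.2 does not call for 95%.

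It would be tempting to say that the one-sided 5% basis of the design is breached. That goes too far. The sizing concerns PASI change only, SAP 4.1 excludes classical hypothesis testing and SAP 4.2 has no decision rules. No error rate, power figure or listed secondary endpoint moves, and the departure is towards wider intervals. What is at stake is comparability of intervals within the efficacy report.

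**What to change.** First check SAP 8.2.2.2 for a stated level. If it gives 90% or none, extend the statement in SAP 9.2.2 to "LSMEANS TRTPN * VISIT / ILINK COV DIFF CL" followed by `ALPHA=0.1` before the semicolon, and state 90% for binary endpoints in the text. If it gives another level, set that level on LSMEANS and remove the 0.1 from MODEL. Use the same level when the alpha placeholders in SAP 9.2.3 and 9.2.4 are filled in, so that exact and model-based intervals agree.

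The cost is one option in sample code and one sentence of text. No data collection, sample size or other analysis changes.
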